### **5.1.2 Study Treatments**

#### **5.1.2.1 Venetoclax (venclexta)**

Venetoclax (venclexta) is a tan, oval tablet with a “V” debossed on one side and “50” or “100” on the other. The venetoclax 10mg formulation is a tan, round tablet with a “V” debossed on one side and a “10” on the other.

Venetoclax will be obtained as a standard of care therapy by the treating clinician/treatment team. Venetoclax is not provided by the study.

#### **5.1.2.2 Decitabine cedazuridine (DEC-C or INQOVI)**

The DEC-C (INQOVI) tablet is a fixed-dose combination of decitabine 35mg and cedazuridine 100mg for oral administration. The drug product is a red, oval shaped, film-coated, immediate-release tablet. The drug products are either plain faced on both sides or have a debossed marking of “H35” on one side and plain faced on the other.

DEC-C is provided by the study.

## **5.2 Study Drug Dosing and Administration**

### **5.2.1 Dosing Instructions for Patients**

[figure not shown]
Study medications will be dosed according to the schedules provided below and in [Figure 1](#) and [2](#). For doses of oral medications to be taken on non-clinic days, patients will be provided with medication to take home.

#### **5.2.1.1 Venetoclax**

Venetoclax should be taken with food and water at the same time each day, generally within 30 minutes of a meal. The tablets should be swallowed whole and not crushed or broken. Patients should drink 6-8 glasses of water daily for two days before initiating therapy with venetoclax and during the escalation period. On days that venetoclax is taken with DEC-C, venetoclax should be taken with breakfast at least 2 hours after DEC-C is taken.

Each patient is scheduled to receive oral venetoclax per the dosing schedule in [Figure 3](#), beginning with an initial dose ramp period during Cycle 1. On the first 2 days of initial treatment (e.g. Week 1 of Cycle 1), each patient's daily dose of venetoclax is scheduled to be 100mg and then 200mg. Beginning on day 3, each patient is scheduled to continue oral venetoclax on a continuous schedule of 400mg daily.

In the absence of unacceptable adverse event requiring dose reduction, it is intended that all patients will receive venetoclax by the same dose and schedule. Patients will take venetoclax tablets with a meal and water at approximately the same time each day. Venetoclax tablets should be swallowed whole and not chewed, crushed, or broken prior to swallowing.

**Figure 3.** Dose ramp and steady state dosing during cycle 1 of pre-remission phase.

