### 1.3.1 Dose Schedule and Rationale

#### 1.3.1.1 Venetoclax dosing

All patients who initiate therapy on this study will have venetoclax ramped to a dose of 400mg/day. In the dose de-escalation phase of this study, venetoclax will be dosed continuously in 28 day cycles in dose level 1 and dose level -1. In dose level -2,

venetoclax will be dosed 21/28 days. This dosing was selected based on the FDA label in treatment naïve AML. Dose modifications follow the venetoclax US Prescribing Information.

For additional information regarding venetoclax dosing, see [Figure 1](#) and [2](#).

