**Pre-remission phase:**

Dose Level 1:      DEC-C 100mg/35mg on days 1-5  
                         Venetoclax 400mg/day x 28 days

Dose Level -1:      DEC-C 100mg/35mg on days 1-4  
                         Venetoclax 400mg/day x 28 days

Dose Level -2:      DEC-C 100mg/35mg on days 1-4  
                         Venetoclax 400mg/day x 21/28 days

Three initial patients will be enrolled at dose level 1 during the pre-remission phase of treatment. If there are 0 dose limiting toxicities (DLTs), then enrollment will proceed at this dose level. If there is 1 DLT, then 3 additional subjects will be enrolled. If  $\geq 2$  DLTs in six patients, dose level -1 will be evaluated using a similar approach, followed by dose level -2. See [Table 4](#).

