**Table 5: Venetoclax/DEC-C Dose Level Summary (Pre-remission Phase)**

DOSE LEVEL	VENETOCLAX	DEC-C
1	400mg once daily Continuous Day 1-28 Δ	100mg/35mg once daily Days 1-5
-1	400mg once daily Continuous Day 1-28 Δ	100mg/35mg once daily Days 1-4
-2	400mg once daily Continuous Day 1-21 Δ	100mg/35mg once daily Days 1-4

\* Cycles are every 28 days.

Δ Venetoclax dosing will be ramped on C1D1 and C1D2 per [Figure 3](#).

During the pre-remission phase, it is intended that venetoclax will be dosed continuously per the dose level summary ([Table 5](#)) and will not be interrupted unless the day C1D22 BMBx is negative for leukemia. Missed days of venetoclax due to treatment interruption in a patient with aplastic marrow that is negative for AML, who are otherwise tolerating therapy well and without evidence of a DLT, will not influence evaluability (i.e., required minimum number of venetoclax doses).

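### Section 5.2.1.1 states one continuous venetoclax schedule for all patients, in conflict with the 21-of-28-day schedule set elsewhere for pre-remission dose level -2

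*Combined protocol and SAP*

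**What the plan says.** Section 5.2.1.1 belongs to the dosing instructions for patients. For the first two days, "each patient's daily dose of venetoclax is scheduled to be 100mg and then 200mg". After that, "Beginning on day 3, each patient is scheduled to continue oral venetoclax on a continuous schedule of 400mg daily". The next paragraph reads: "In the absence of unacceptable adverse event requiring dose reduction, it is intended that all patients will receive venetoclax by the same dose and schedule". Neither sentence mentions dose level. The section refers to Figure 3, captioned "Dose ramp and steady state dosing during cycle 1 of pre-remission phase", which is not available in the text reviewed.

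Three other places define pre-remission level -2 differently:

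- Section 1.3.1.1 has continuous dosing at levels 1 and -1. For level -2, "venetoclax will be dosed 21/28 days".
- Section 5.2.2 lists level -2 as "Venetoclax 400mg/day x 21/28 days".
- Table 5 gives level -2 as "400mg once daily Continuous Day 1-21".

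Section 5.2.4 sets the venetoclax minimum for DLT evaluability at 75% of first-cycle doses and gives both 21/28 and 16/21 as examples. Section 1.3.1.2 and Table 5 give DEC-C on days 1-4 at both level -1 and level -2.

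**The concern.** A patient newly enrolled at level -2 is there because of DLTs in other patients (Section 5.2.2, Table 4). That patient has had no adverse event, so the exception in Section 5.2.1.1 does not clearly apply. One part of the protocol then says continuous dosing on the same schedule as everyone else, and three other parts say 21 of 28 days.

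This matters for dose finding because venetoclax duration is all that separates levels -1 and -2 before remission. If a site took Section 5.2.1.1 literally, a cohort labelled level -2 would receive the level -1 regimen. Its DLT count would be a second look at level -1, and a level -2 RP2D would not describe what was given. The 75% dose check would also have two possible denominators.

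**Working it through.** **1. The protocol's own minima.** Scheduled days come from Table 5 and the 75% rule from Section 5.2.4.

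- 0.75 × 28 = 21
- 0.75 × 21 = 15.75, rounded up to 16

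Both stated examples (21/28 and 16/21) reproduce, so Section 5.2.4 assumes that a 21-day schedule exists.

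**2. Pre-remission schedules side by side.** Cycle 1 venetoclax = 100 + 200 + 400 × (days − 2) mg. A second pre-remission cycle = 400 × days mg.

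| | Venetoclax days | DEC-C days | Cycle 1 mg | Cycle 2 mg | 75% minimum |
|---|---|---|---|---|---|
| Level -1 | 28 | 4 | 10,700 | 11,200 | 21 |
| Level -2 per 1.3.1.1, 5.2.2, Table 5 | 21 | 4 | 7,900 | 8,400 | 16 |
| Level -2 if 5.2.1.1 is read literally | 28 | 4 | 10,700 | 11,200 | 21 |

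The third row equals the first. The gap between the two readings of level -2 is 7 days, or 7 × 400 = 2,800 mg per cycle. That is 2,800/10,700 = 26% of cycle 1 and 2,800/11,200 = 25% of cycle 2.

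**3. Effect on the dose count.** A level -2 patient who takes 16 to 20 doses meets the 16/21 minimum but not the 21/28 minimum. For example, 16 doses is 16/21 = 76% on one schedule and 16/28 = 57% on the other. Section 5.2.4 also counts missing more than 25% of venetoclax doses for related adverse events as a DLT. With 21 planned days, that means 6 or more missed doses (25% = 5.25). With 28 planned days, it means 8 or more (25% = 7). The same number of doses taken, from 16 to 20, can therefore be classified differently.

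**4. How often level -2 would open.** Under Table 4, P(a level is abandoned) = P(≥2 DLTs in 3) + P(1 in 3) × P(≥1 in the next 3).

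- DLT rate 20%: 0.104 + 0.384 × 0.488 = 0.291
- DLT rate 30%: 0.216 + 0.441 × 0.657 = 0.506
- DLT rate 40%: 0.352 + 0.432 × 0.784 = 0.691

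Level -2 opens only if levels 1 and -1 are both abandoned. Taking the two as independent with equal rates, the chance is the square: 0.085, 0.256 and 0.477. The 20% rate is the ceiling used for toxicity monitoring in Section 9.3.1. The 30% and 40% rates, and equality across levels, are assumptions. Equality ignores any benefit from the shorter DEC-C course at level -1.

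**The case against.** The strongest reply is that sites have other instructions. Every Cycle 1 and Cycle 2 visit list in Sections 7.3 and 7.4 tells them to dose by Tables 5 and 6, and none cites Section 5.2.1.1 for the schedule. Misdosing would require a site to put Section 5.2.1.1 above Sections 1.3.1.1 and 5.2.2, Table 5, the 16/21 example and the visit lists. This stands, and it limits the practical risk considerably.

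Second, the wording has a compatible reading. Table 5 describes level -2 as "400mg once daily Continuous Day 1-21", and the text below it ties continuous dosing to the dose level summary. Continuous could therefore mean without a break within the level's planned days. This stands in part: Section 1.3.1.1 uses the word in contrast to 21 of 28 days, and the reading does not account for the statement that all patients share one schedule. Table 1 likewise shows continuous daily dosing after the ramp with no mention of dose level. Figures 1 to 3 might carry the distinction, but they could not be checked.

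Third, the 7-day gap is a maximum for cycle 1. The disputed days are 22-28, and the marrow is taken on day 22. Venetoclax is interrupted when that marrow is aplastic and free of leukemia (Table 5 text and the post-remission text in Section 5.2.6.3), so for those patients much of the gap may never arise. This stands.

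A reader might also infer more than the documents support:

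- **That the protocol has removed the difference between levels -1 and -2.** It has not. Three concordant passages and the 16/21 rule keep it, and it disappears only if Section 5.2.1.1 overrides them.
- **That the two levels coincide throughout treatment.** In the post-remission phase (Table 6) they differ in both drugs.
- **That patients would stay on a regimen already judged too toxic.** Level -2 in dose finding is a new cohort.
- **That 8% to 48% is the chance of misdosing.** Those figures give only the chance that level -2 opens, under assumed rates.

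**Conclusion.** The conflict is real but minor. Section 5.2.1.1 is operative text with no dose-level qualifier, and on its face it disagrees with Sections 1.3.1.1 and 5.2.2 and Table 5 for pre-remission level -2. If followed literally, it would make level -2 identical to level -1: up to 7 more venetoclax days (2,800 mg) per cycle than the level -2 entries give, and a 75% minimum of 21 doses instead of 16.

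The consequence depends on two conditions: level -2 must open, and a site must follow Section 5.2.1.1 over the tables that the visit lists cite. The documents give no basis for a probability on the second. The type I error rate, power, sample size and primary endpoint are unaffected. The conclusion rests on the text alone, since Figures 1 to 3 were not available, and it takes no view on which schedule is right.

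**What to change.** Reconcile Section 5.2.1.1 and the patient dosing diary with Sections 1.3.1.1 and 5.2.2, Table 5 and the dose-count denominators in Section 5.2.4, so that one venetoclax schedule is stated for each dose level. When doing so, check that Table 1 and Figures 1 to 3 agree, and keep the pre-remission levels (Table 5) distinct from the post-remission levels (Table 6). The sponsor decides which schedule applies at each level.

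The cost is the wording of two sentences in Section 5.2.1.1 plus matching diary text. Section 10.1 requires a written amendment with approval by the study chair and the local IRB, so the change could be made together with other corrections. No statistical recalculation is needed.

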### Missed Doses

If a dose is missed within 8 hours of the time it is usually taken, the subject should take the missed dose as soon as possible. If a dose is missed by more than 8 hours, the subject should not take the missed dose. In either scenario, the subject should resume the usual dosing schedule the next day.

### Vomited Doses:

If the subject vomits after dosing, the vomiting episode and the time it occurred should be recorded in the dosing diary. No additional dose should be taken that day. The next prescribed dose should be taken at the usual time. Investigators should consider pre-medicating the subject with antiemetics if vomiting is anticipated to be a recurring issue.

#### 5.2.1.2 Oral Decitabine and cedazudridine

Oral decitabine-cedazuridine (DEC-C) should be taken at the same time each day, typically in the morning. Patients should have an empty stomach with no food for 2 hours before and at least two hours after administration. Anti-acid medications should be taken at night. The tablets should be swallowed whole and not crushed or broken.

### Missed Doses

If a dose is missed within 12 hours of the time it is usually taken, the subject should take the missed dose as soon as possible. If a dose is missed by more than 12 hours, the subject should not take the missed dose. In either scenario, the subject should resume the usual dosing schedule the next day and proceed with completing the entire number of planned treatment days per cycle.

**Vomited Doses:**

If the subject vomits after dosing, the vomiting episode and the time it occurred should be recorded in the dosing diary. No additional dose should be taken that day. The next dose should be taken at the usual time. Investigators should consider pre-medicating the subject with antiemetics if vomiting is anticipated to be a recurring issue.

**5.2.1.3 Venetoclax/DEC-C combination therapy:**

On days involving dosing of both venetoclax and DEC-C, the DEC-C should be taken orally (PO) daily on an empty stomach (morning before breakfast) with no food for 2 hours before and at least 2 hours after administration. Venetoclax should be taken daily with breakfast at least 2 hours after DEC-C.

In the post-remission phase of the study, patients may take venetoclax with a meal and the DEC-C at bedtime (with an empty stomach). Both agents should be taken at approximately the same time each day.

A dosing diary will be used to enhance compliance.

**5.2.2 Dose Schedules for Evaluation (Pre-remission Phase only)**

The study will follow a dose de-escalation design. Cycles are 28 days.

**Pre-remission phase:**

Dose Level 1:      DEC-C 100mg/35mg on days 1-5  
                         Venetoclax 400mg/day x 28 days

Dose Level -1:      DEC-C 100mg/35mg on days 1-4  
                         Venetoclax 400mg/day x 28 days

Dose Level -2:      DEC-C 100mg/35mg on days 1-4  
                         Venetoclax 400mg/day x 21/28 days

Three initial patients will be enrolled at dose level 1 during the pre-remission phase of treatment. If there are 0 dose limiting toxicities (DLTs), then enrollment will proceed at this dose level. If there is 1 DLT, then 3 additional subjects will be enrolled. If  $\geq 2$  DLTs in six patients, dose level -1 will be evaluated using a similar approach, followed by dose level -2. See [Table 4](#).

**Table 4: Dose De-escalation Rules**

Number of Patients with Drug-Related DLT at a Given Dose Level	Dose De-escalation Step
0 of 3	Proceed as RP2D
1 of 3	Treat 3 more patients at the same dose level
$\geq 2$ of 3	Enrollment at this dose level stops. Proceed to next lower dose level
$\leq 1$ of 6	Proceed as RP2D
$\geq 2$ of 6	Proceed to next lower dose level

All patients will be considered evaluable for DLT unless they cannot complete the first cycle of therapy due to withdrawal of consent or disease progression. A patient who is not DLT-evaluable will be replaced. Cohort review discussions will be held between the study chair and other investigator(s) to confirm dose escalation, reductions, and cohort expansions.

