### 5.2.4 Dose-Limiting Toxicity

A dose-limiting toxicity (DLT) is defined as any toxicity that occurs up to day 28 during the dose de-escalation (pre-remission) phase and is at least possibly related to study drug administration. This does not include toxicity with a clear alternative explanation (e.g., disease progression) or transient ( $\leq 72$  hours) abnormal laboratory values without

associated clinically significant signs or symptoms based on investigator determination. All DLTs will be assessed by the investigator using CTCAE v5.0 criteria.

To be considered evaluable, subjects must fulfill the following minimum criteria:

- All doses of DEC-C.
- 75% of doses of venetoclax during the first cycle (e.g., 21/28 or 16/21 days)

All patients who initiate venetoclax/DEC-C, receive at least one dose of each, and experience a DLT are evaluable regardless of whether the minimum criteria above are met.

Subjects experiencing toxicity that results in dose-holds will remain evaluable provided the minimum criteria outlined above are met. Patients that require dose reductions during the DLT evaluation period (e.g., first 28 days after initiation of the first dose of study treatment/C1D1) will not be considered a DLT so long as they receive the minimum doses at the prescribed dose level outlined above.

Patients who achieve a morphologic remission on C1D22 BMBx, have not experienced a DLT, and have treatment interrupted due to favorable treatment response will be considered evaluable if they complete 75% of protocol-directed doses (i.e., a patient who achieves a remission and is instructed to stop venetoclax on C1D24 is considered evaluable provided they received at least 18/24 venetoclax doses, or 75%) and will not be replaced.

Patients missing >25% of venetoclax doses, or any DEC-C doses due to adverse event(s), will be considered a DLT provided the AEs are considered related. If unrelated, the patient may be replaced as described above.

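### DLT evaluability is defined inconsistently, so the 3 and 6 patients behind the Table 4 decisions are not fixed

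*Combined protocol and SAP*

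**What the plan says.** Five places in the combined protocol and SAP bear on who counts for DLT.

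- **Section 5.2.2, text under Table 4.** "All patients will be considered evaluable for DLT unless they cannot complete the first cycle of therapy" because of consent withdrawal or progression. No minimum dose is given. Replacement is mandatory: "A patient who is not DLT-evaluable will be replaced".
- **Section 5.2.4, opening text.** "To be considered evaluable, subjects must fulfill the following minimum criteria": all DEC-C doses, and 75% of venetoclax doses in cycle 1. Patients who start treatment, take at least one dose of each drug and "experience a DLT are evaluable regardless of whether the minimum criteria above are met". On shortfalls: "Patients missing >25% of venetoclax doses, or any DEC-C doses due to adverse event(s), will be considered a DLT provided the AEs are considered related". Replacement is optional when the adverse event is unrelated. A patient stopped early for remission needs 75% of the doses due up to the stop (example: 18 of 24).
- **Section 5.2.4, Exceptions.** A patient withdrawn from the study before day 28 for any non-DLT reason is not evaluable for DLT and must be replaced. A patient who stops treatment for clearly unrelated reasons below the dose minimum may be deemed not evaluable for *response*, and replaced.
- **Section 5.2.6.3, text under Table 5.** Venetoclax days missed through interruption for an aplastic, AML-negative marrow, in a patient tolerating therapy without a DLT, do not affect evaluability. No 75% floor is mentioned.
- **Section 9.3.1 and Table 10.** Bayesian monitoring starts when the sixth patient is evaluable for toxicity, but the worked example and the table heading count patients treated.

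**The concern.** Table 4 can declare the RP2D on 0 of 3, or on at most 1 of 6. With so few patients, who enters the denominator matters as much as the cut-off. The two main rules give different denominators for the same patient, and no sentence ranks one above the other.

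The situation is foreseeable. Section 5.2.6.1 interrupts both drugs for Grade 4 infection, clinical sepsis or neutropenic fever, and a vomited dose is not retaken (Section 5.2.1). One lost DEC-C dose is enough to fail the Section 5.2.4 minimum. If the gap is judged unrelated to study drug, the patient is a clean observation under one rule and not evaluable under the other. Left open, the choice would be made case by case after the outcome is known.

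**Working it through.** **1. The plan's own figures.** 75% of 28, 21 and 24 days is 21, 15.75 (rounded up to 16) and 18, as Section 5.2.4 states. With a Beta(1,1) prior, a limit of 0.20 and a posterior probability above 80%, all eight Table 10 boundaries reproduce: the posterior probability lies between 0.804 and 0.854, for example 0.852 at 2 of 6. The figures are sound; the inconsistency is in the definition.

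**2. The rules side by side.**

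| Patient in cycle 1 | Text under Table 4 | Section 5.2.4 |
|---|---|---|
| Below minimum, related AE | no separate rule | DLT |
| Does not complete the cycle: progression, or consent withdrawal without a DLT | not evaluable, replaced | not evaluable; if withdrawn from the study before day 28, replaced |
| On study, below minimum for an unrelated AE, non-adherence or logistics | evaluable, DLT-free | not evaluable; for an unrelated AE, replacement optional |
| DLT after at least one dose of each drug, then consent withdrawn | not evaluable, replaced | evaluable, DLT |

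The last two rows conflict. In both, the Table 4 text lowers the DLT count relative to the patients counted. For example, one DLT in three reads as 0 of 3 if that patient is dropped and the replacement is DLT-free.

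**3. Size of the under-dosing effect.** Inputs from the plan: Table 4 accepts a level on 0 of 3, or on 1 of 3 followed by 0 of 3. Assumptions, not in the documents: true DLT rate *p* of 0.33 or 0.40; exactly one of the first three patients under-dosed, with DLT risk *q*; the second three fully dosed.

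P(0) = (1−p)²(1−q)

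P(1) = 2p(1−p)(1−q) + (1−p)²q

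P(accept) = P(0) + P(1)(1−p)³

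| | q = p (fully dosed) | q = p/2 | q = 0 (upper bound) |
|---|---|---|---|
| p = 0.33: P(0) | 0.301 | 0.375 | 0.449 |
| p = 0.33: P(accept) | 0.301 + 0.444×0.301 = 0.434 | 0.375 + 0.443×0.301 = 0.508 | 0.449 + 0.442×0.301 = 0.582 |
| p = 0.40: P(0) | 0.216 | 0.288 | 0.360 |
| p = 0.40: P(accept) | 0.216 + 0.432×0.216 = 0.309 | 0.288 + 0.456×0.216 = 0.386 | 0.360 + 0.480×0.216 = 0.464 |

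If the under-dosed patient keeps 80% of full risk, acceptance is 0.464 at p = 0.33 and 0.340 at p = 0.40.

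**4. Backstop.** Take a level accepted on 0 of 3, count those three patients toward Table 10 and assume all later patients are fully dosed. The probability of a pause by patient 14 is 0.595 (p = 0.33) or 0.759 (p = 0.40). By patient 34 it is 0.866 or 0.967.

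**The case against.** A reader might infer that the Table 4 rule counts under-dosed patients in general as DLT-free. The documents do not support that. Shortfalls from related adverse events are DLTs, and withdrawals and progressions are replaced. What remains is a patient still on study with a shortfall for another reason, and only if the Table 4 text overrides Section 5.2.4. Nor does Section 5.2.4 always replace such a patient: for an unrelated adverse event it only permits replacement.

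A case can be made that Section 5.2.4 governs. Section 9.3.1 cites it for DLT, and so does note 4 to the schedule tables. Those pointers concern what a DLT is, however, and do not say who is in the denominator of Table 4, whose own sentence gives a different answer.

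A reader might also take the rise from 43% to 58% as the expected effect. It assumes that the under-dosed patient cannot have a DLT, which is extreme: missing one of five DEC-C doses fails the minimum, yet dose level −1 itself gives DEC-C on days 1-4 and is assessed for DLTs.

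Table 10 would probably pause a falsely accepted level. That stands, but it acts only from the sixth patient, after further patients have been exposed, and its own denominator is ambiguous.

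**Conclusion.** Wrong as written. The text under Table 4 and Section 5.2.4 cannot both define the 3 and 6. The Exceptions text, the text under Table 5 and the evaluable/treated wording around Table 10 add further inconsistency. Followed literally, the Table 4 sentence can give a wrong count for the RP2D decision, and both conflicting cases favour accepting a toxic level.

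The affected group is narrow and its frequency unknown. Given one under-dosed patient among the first three, acceptance rises by about 7 to 8 percentage points at half risk and by about 15 at zero risk, for true DLT rates of 33% and 40%. These are conditional figures over an assumed range, not estimates for this trial.

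**What to change.** 1. Keep one DLT-evaluable definition in Section 5.2.4: the patient had a DLT after at least one dose of each drug, or met that section's minimum exposure.
2. Replace the evaluability sentence under Table 4 with a reference to that definition.
3. Reconcile the remission-interruption provisions of Section 5.2.4 and the text under Table 5 within it. Simply replacing everyone below the minimum could remove patients whom the Table 5 text keeps evaluable.
4. Settle whether replacement is mandatory or optional, and use one verb throughout.
5. In the Exceptions text, change evaluable for response to evaluable for DLT, if that is what is meant.
6. Use the same denominator in Section 9.3.1 and Table 10 instead of mixing evaluable and treated.

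The cost is a short text amendment, with no change to any dose level or boundary. The downside is an occasional replacement patient in dose finding, which the protocol already allows.
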